9.2 Design

The focus of this study is to determine the difference in mental health parameters following the participation of cancer patients in a creative writing workshop. Participants will be randomized within strata formed by cancer type in order to assure that these potentially important confounding variables are balanced across groups. Patients will be enrolled on a rolling basis over a four to five-month period, allowing patients in intervention arm to participate in 2-3 months workshops (workshops would be held once every 2 weeks). Patients in control arm will be provided a book (*Writing Down Bones* by Natalie Goldberg) about creative writing and will be asked to do activities for 1.5 hours every 2 weeks. After three months, control group participants can join creative writing workshops at their discretion for the remaining period for writing workshops. Both group members will receive follow up surveys twice a month for two months at the completion of the participant's two-month study period.

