10.0 STUDY PROCEDURES

10.1 Methods: After enrollment as above, co-investigators of this study or the assigned coordinator will be doing the consent. Patient will be randomized to intervention and control arms in a 2:1 ratio. The intervention arm will receive a dedicated workshop for one and a half hours every 2 weeks. We aim to start a 6 month long program with weekly creative writings workshops, and patient enrollment in the study will continue through the 1st 4.5 months of the 6 month period so that the last enrolled patient could complete 2 classes per month for two months. Each patient will be asked to attend at least two classes per month for a total of two months. These workshops will be held at Hershey Medical Center (HMC). At the initiation of the study along with consent we will collect baseline scores in both groups for each parameter as below. Somatic Symptom Burden (SSM-8 - Figure 2 - reference section), depression symptoms using PHQ-9 (Figure 3 – reference section), and anxiety symptoms using GAD-7 (Figure 4 – reference section) will be collected monthly and following intervention completion.

We will collect mood scores pre and post each session. We will use Emotional Thermometer Scale (EMS) from [name] (Feb. 2010), diagram for scales is shown in figure 1. Please see supplementary index for a letter of permission to use from [name]. We will give the Thermometer scales and collect scores pre and post each session and also collect scores pre and post completion of entire course. Control group will do EMS on monthly basis along with other parameters. At the end of the study we will review all participants' medical charts to count view the number of emergency room visits and hospitalizations each participant experienced during the study period. These will be further broken down in categories based on cancer

Institutional Review Board

related vs non-cancer related visits. We will also review their most current cancer disease status after completion of the workshops and categorize whether their status is considered to be stable, progressing, or in remission. Both groups will also receive follow up mood and symptom surveys twice a month for up to 2 months after completion of the participant's two to three month study period.

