The control arm will receive a book (i.e., *Writing Down Bones* by Natalie Goldberg) on creative writing and asked to read and do writing activities for one and a half hours once every two weeks. At the completion of the two-month participation or completion of 4 sessions control patients will be given the opportunity to enroll in the creative writing workshops for the remainder of the study period of 6 months. We will collect scores from control arm through the same Emotion Thermometers Scale on a monthly basis. Pre-intervention scores will be obtained at the time of consent or one week prior to the planned start of session 1 for workshop (either in the clinic if possible or mail the score sheet to patients with an enclosed stamped envelope for return of the scales). Depending on participant preference, we can send them emails of the REDCAP surveys containing the same information at set intervals. A sample of the REDCAP surveys is included in supplementary materials. We will also send participants in the control arm a stamped return envelope on a monthly basis if not able to get score sheets in a clinic or over REDCAP, depending on patient convenience and preference. We will call the participants once every 3-4 weeks to check in on their progress. Please see a calendar at the end for details.

To assess for possible confounding results of patients participating in the concurrent exercise study, we will ask participants if they are also enrolled in the exercise study at enrollment and perform a subset analysis for patients who are in the exercise study. They will be randomized into either control or intervention group in the same manner as the other patients in the study. We will additionally include a section of the survey to ask about regular exercise (more than 30 minutes, three times a week) and do a subset analysis of these patients as well.

We will be collaborating with the Department of psychiatry at HMC - [name], [name], and [name]. Any subject who requests psychiatry follow up will be referred to [name]. If participants report the presence of suicidal ideation per question nine on the PHQ-9 [i.e., Thoughts that you would be better off dead or of hurting yourself in some way], they will be referred on an urgent basis to [name] or [name]. In the event [name] and/or [name] are unavailable for follow-up, If any active suicidal thoughts are reported, participants will be referred directly to Emergency Department at Hershey Medical Center.

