10.6 Control group activities: Participants randomized into the control group were asked to maintain their usual follow up while also reading a book on creative writing for one and a half hours every other week for three months, logging their activity for verification of task completion. Their mode scores will be measured as mentioned above.

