11.0 Statistical Plan

11.1 Statistical Analysis Plan

Participants' basic demographic and baseline clinical measurements will be summarized using descriptive statistics. Those summarizations will be based on all patients as well as on patients within each group. This study has several main groups of outcome variables, which reflect several different domains of patient's mental health. The first group is the emotion thermometer (which has five sub-scales), the second is the somatic symptom scale (SSS-8), the third is the Patient Health Questionnaire (PHQ-9), and the fourth is the Generalized Anxiety Disorder questionnaire (GAD-7), which measures participants' anxiety. All the above outcome variable groups are based on questionnaires using Likert-scale questions to take the measurements, and each group may involve multiple sub-dimensions. Both the intervention group and the control group have repeated measures of the outcomes as shown in Figure 1. Graphical methods (such as the line plot of mean/SD values vs. time) will first be used to illustrate the mean and standard deviation values of the mode, depression, and anxiety scores through the time for both groups. These methods will help us detect the patterns of how the scores change over time (within-group change) and how the scores differ between groups. We will further use the linear mixed-effect model for repeated measures to analyze the within-group and between-group differences. Every sub-dimension will be analyzed individually, but we will also analyze the composite score for the dimensions. For the patients in the control group this study involves two stages (week 1-12 and week 13-20), and at the end of the 12th week, they can join the intervention group. This setting will allow us to study the effect of the intervention on the control group alone. For this part of analyses, linear mixed-effect models will be set up with the stage serves as an indicator variable in the model. The comparison of outcome variables between certain time points will also be done using paired tests. We will further investigate the possible factors that might affect the change of outcome variables over time. The factors are gender, race, marital status, time from cancer diagnosis (first 3 months, 3-6 months, more than 6 months) and cancer stages. This part of analyses will mainly be focused on the intervention group and the above factors will be examined in the linear mixed-effect models. All analyses will be performed using statistical software SAS version 9.4 or higher (SAS Institute, Cary, NC, USA) and the statistical significance level to be used is 0.05.

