
11.2 Sample size considerations:

We plan to enroll a total of 60 participants in the study – with 40 participants in the intervention group and 20 participants in the control group (2:1 ratio). This sample size is mainly determined by the capacity of the workshop. With this sample size we are able to detect a standard effect size (the mean difference measured in common standard deviation) of 0.45 with at least 80% statistical power (using two-sample repeated measure ANOVA model, assuming four time-points, and the within-patient auto-correlation being 0.2) .

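### The 80% power at 0.45 SD in section 11.2 holds on one unstated reading only (four post-randomisation scores under AR(1)), and the visible PHQ-9 and GAD-7 schedule gives two to four scores before controls may join the workshops

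*Combined protocol and SAP*

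**What the plan says.** Section 11.2 fixes 40 intervention and 20 control patients, mainly because of workshop capacity, and claims that this detects a standardised effect "of 0.45 with at least 80% statistical power (using two-sample repeated measure ANOVA model, assuming four time-points, and the within-patient auto-correlation being 0.2". It does not name the outcome, the contrast, the four time-points, their spacing, the correlation structure or the sidedness, and it makes no allowance for dropout. Section 11.1 sets the significance level at 0.05 and plans a linear mixed model for repeated measures. It names no primary contrast and does not mention baseline adjustment.

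PHQ-9 and GAD-7 are primary endpoints (9.4.1). After a baseline score taken around consent, they "will be collected monthly and following intervention completion" (10.1).

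The documents give two different times at which controls may enter the workshops:

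- Section 10.1: "At the completion of the two-month participation or completion of 4 sessions control patients will be given the opportunity to enroll".
- Section 9.2: "After three months, control group participants can join creative writing workshops at their discretion". Section 11.1 agrees: "at the end of the 12th week, they can join the intervention group". Section 10.6 also has the control activity running "every other week for three months, logging their activity for verification of task completion".

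The emotion thermometers follow another schedule (10.1). For the workshop arm, "We will collect mood scores pre and post each session"; for the other, "Control group will do EMS on monthly basis along with other parameters".

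**The concern.** Power from a repeated-measures comparison depends on how many scores carry the randomised contrast. A baseline score carries none of it, and scores taken after controls may join the workshops no longer protect it. If the schedule gives fewer than four usable scores, section 11.2 promises more than the trial delivers on two of its primary outcomes.

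This matters most for a null result. A reader of 11.2 would take a null PHQ-9 or GAD-7 finding as having had at most a 20% chance of missing a 0.45 SD benefit. With two usable scores that chance is about 45%, and with three it is 31% to 34%.

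**Working it through.** **Inputs.** From 11.2: 40 and 20 patients, effect 0.45 SD (so SD = 1), four time-points, correlation 0.2. From 11.1: alpha 0.05. Assumed: two-sided test, all 60 patients complete, 0.2 between adjacent scores, unadjusted difference in each patient's mean over k scores.

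**Formulas.** Variance of a patient's mean of k scores:

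- Compound symmetry (CS): v = (1 + (k − 1) × 0.2)/k.
- AR(1): v = [k + 2 Σ (k − j) × 0.2^j]/k², summed over j = 1 to k − 1.

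SE = √(v × (1/40 + 1/20)) = √(0.075v). Normal-approximation power = Φ(0.45/SE − 1.960). The t figure uses the non-central t with 58 df.

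**The plan's own figure.** Four post-randomisation scores under AR(1): v = [4 + 2(0.6 + 0.08 + 0.008)]/16 = 0.336. SE = √0.0252 = 0.1587. 0.45/0.1587 = 2.835. Φ(0.875) = 80.9%; t, 79.6%. This reproduces the stated 80%.

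**Other readings of the four time-points.**

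- CS: v = 1.6/4 = 0.400, SE = 0.1732, power 73.8% (normal) or 72.4% (t).
- Baseline as one of the four: the mean effect falls to 0.45 × 3/4 = 0.3375. Power (t) is 55.2% under AR(1) and 48.3% under CS.

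**Power by number of usable scores.**

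| k | Structure | v | SE | Power, t (normal) | Effect at 80% power, t |
|---|---|---|---|---|---|
| 2 | either | 0.600 | 0.2121 | 55.0% (56.4%) | 0.60 SD |
| 3 | AR(1) | 0.431 | 0.1798 | 69.2% (70.6%) | 0.51 SD |
| 3 | CS | 0.467 | 0.1871 | 65.7% (67.2%) | 0.53 SD |
| 4 | AR(1) | 0.336 | 0.1587 | 79.6% (80.9%) | 0.45 SD |
| 4 | CS | 0.400 | 0.1732 | 72.4% (73.8%) | 0.49 SD |

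**Scores the visible schedule supplies for PHQ-9 and GAD-7 before controls may join** (the last one taken before the patient joins):

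| Rule for joining | Completion score is the last monthly score | Completion score is separate |
|---|---|---|
| Two months or 4 sessions (10.1) | 2 | 3 |
| Three months or week 12 (9.2, 11.1) | 3 | 4 |

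Only the bottom-right cell, and only under AR(1), returns about 80%.

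**Sensitivity.**

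- Contrast: if it is a single completion score, v = 1, SE = √0.075 = 0.2739, and power is about 37%.
- Baseline adjustment at 0.2: 56% (AR(1)) to 58% (CS) for k = 2, and 70% for k = 3.
- Spacing: if 0.2 is the two-week AR(1) correlation, the monthly one is 0.2² = 0.04. Power is then 61% (k = 2) and 78% (k = 3).

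**The case against.** The strongest reply is that 11.2 contains no calculation error. AR(1) is a natural reading of its wording, and on its stated inputs the figure reproduces. That stands. A reader might infer that the arithmetic is wrong; it is not. The open question is whether the schedule supplies those inputs.

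The section 10.1 wording can also be read as naming two occasions, so the completion score may be separate from the last monthly one. With the 12-week stage in 11.1, that gives four scores and the stated power under AR(1). This stands too. It does not rescue the two-month or 4-session rule, where a separate completion score brings the count only to three.

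The schema (9.5) and the calendar cited in 10.1 were not visible in the text reviewed, and either could settle the count. They are not missing from the plan, but they must be checked before any count is final.

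Other routes to 80% exist, but none is stated:

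- One-sided 0.05 gives 82.2% (t) for four scores under CS, and 79.6% (t) or 80% (normal) for three under AR(1). No section plans a one-sided test.
- Baseline adjustment with three scores under CS reaches 71% at an assumed correlation of 0.5 and 83% at 0.7. Under AR(1) at 0.5 it gives 61%. Section 11.2 assumes 0.2.
- The twice-monthly surveys after the participation period add scores. They are a secondary endpoint (9.4.2) and fall when controls may already have joined. Joining is optional, so some of these scores stay uncontaminated, but they cannot be counted on.

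**Conclusion.** The concern holds in a conditional form. At two-sided 0.05 with 40 and 20 complete patients and no baseline adjustment, the claim in 11.2 needs four post-randomisation scores, each carrying the full 0.45 SD, under AR(1) at 0.2.

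- Under the two-month or 4-session rule, 80% is not reached: 55% with two scores, or 69% (AR(1)) or 66% (CS) with three.
- Under the three-month or week-12 rule, power is 69% or 66% with three scores. With four it is about 80% under AR(1) and 72% under CS.

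A reader might conclude that power for PHQ-9 and GAD-7 simply is 55% to 69%. The documents do not support that as a settled figure. The count depends on the contradictory durations, on the status of the completion score, and on a schema and calendar not seen here. The percentages also assume a contrast (the mean of post-baseline scores) that the plan does not define. Nor does the point show that 60 patients are too few to proceed with: capacity sets that number, and what needs correcting is the power statement.

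**What to change.** Keep 60 patients, and take these steps in order.

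1. Reconcile the two-month or 4-session text in 10.1 with the three-month or week-12 text in 9.2, 10.6 and 11.1, and check both against the schema and calendar. This review takes no position on which is right.
2. State whether the completion score is separate from the last monthly score.
3. In 11.1 and 11.2, name the primary contrast, whether baseline is adjusted for, the sidedness, the correlation structure and the interval to which 0.2 applies.
4. Restate in 11.2 the power at 0.45 SD and the effect detectable with 80% power for that contrast. If it is the unadjusted mean of k post-baseline scores taken before controls may join, the matching row of the working table supplies both. If it is a single completion score or a baseline-adjusted mean, start from the sensitivity figures instead.
5. Give the thermometer power in its own sentence with the number of scores per arm. The arms are scored at different frequencies, so a single k does not apply.

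The cost is wording in 11.1 and 11.2 once the durations are reconciled, with no extra patients or visits. On most readings the stated power becomes less favourable.

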9.4 Endpoints:**9.4.1 Primary endpoints:**

- Mood scores before (at baseline) and after intervention (after completion of entire sessions - this may vary as some patients may not be able to complete six sessions). A validated Emotional Thermometer Scales will be used to predict changes in parameters pre and post-intervention.
- Severity of depression and anxiety symptoms before and after intervention between two groups. Validated Depression and Anxiety questionnaires will be used to predict changes, the PHQ-9 and GAD-7 respectively.

9.4.2 Secondary endpoints:

[figure not shown]
- Mood and symptoms before and after at least 2 sessions of intervention.
- Self-reported somatic symptoms pre and post intervention in two groups. We will use the Somatic Symptom Scale – 8 (SSM-8) to quantify somatic symptom burden.
- Difference in scores and symptoms between various genders.
- Difference in scores and symptoms between patients living alone versus with family.
- Difference in scores and symptoms in different cancer types.
- Difference in scores and symptoms versus number of classes attended.
- Differences between individual mood scores for patients in the control group who later switch to intervention group and attend at least one session
- Mood and symptom scores up to 2 months after completion of the study.

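### The 80% power in section 11.2 does not belong to the before-versus-after primary endpoints of section 9.4.1; at a correlation of 0.2 those have roughly 21-25% (raw change) or 37-38% (completion score) power

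*Combined protocol and SAP*

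**What the plan says.** Section 11.2 contains the only power statement. It plans a trial "with 40 participants in the intervention group and 20 participants in the control group (2:1 ratio"), says the size is set mainly by workshop capacity, and states that this detects "a standard effect size (the mean difference measured in common standard deviation) of 0.45" "with at least 80% statistical power". The basis is "using two-sample repeated measure ANOVA model, assuming four time-points, and the within-patient auto-correlation being 0.2". It does not say which effect in that model is tested, whether baseline is one of the four time-points, what the correlation structure is, or whether the test is one- or two-sided. Section 11.1 adds only that "the statistical significance level to be used is 0.05".

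Section 9.4.1 gives two primary endpoints. The first is "Mood scores before (at baseline) and after intervention (after completion of entire sessions"), on the Emotion Thermometers. The second, on the PHQ-9 and GAD-7, is "Severity of depression and anxiety symptoms before and after intervention between two groups".

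Section 11.1 will use a "linear mixed-effect model for repeated measures to analyze the within-group and between-group differences", and also paired tests between certain time points. It does not say which contrast carries the primary conclusion.

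The same sample-size text stands in the two earlier protocol versions in the file, numbered 12.2 and 13.2 there.

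**The concern.** Power is a property of a specific contrast. Averaging four weakly correlated scores removes much of the noise, so a correlation of 0.2 favours a time-averaged comparison. The same low correlation works against a before-to-after comparison, because a weakly related baseline explains little and subtracting it adds its own noise. A figure computed for the first kind of contrast therefore cannot be attached to the second.

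The risk is in interpretation. If the before-to-after comparison is null, a reader of 11.2 may take it as evidence against a 0.45 SD benefit from a trial with 80% power. On the inputs below, the trial would miss such a benefit more often than it would find it.

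**Working it through.** **Inputs from the plan.** 40 and 20 patients, difference 0.45 SD, four time-points, correlation 0.2 (11.2); significance level 0.05 (11.1).

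**Assumptions of this check.** Two-sided test, complete data, equal variances, independent patients, and 0.45 expressed in SDs of a single score. The structure is unstated, so both compound symmetry (every pair 0.2) and AR(1) (0.2 per step) are shown.

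**Formula.** Let v be the variance of the per-patient contrast in units of SD². The standard error is √(v(1/40 + 1/20)) = √(0.075v), and the noncentrality is 0.45/√(0.075v). Power is from the noncentral t with 58 df (57 with a baseline covariate), with the normal approximation alongside.

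**Step 1: reproduce the 80%.** Contrast: the mean of four scores.
- AR(1): v = [4 + 2(3×0.2 + 2×0.04 + 0.008)]/16 = 5.376/16 = 0.336. Noncentrality 2.835; power 79.6% (normal 80.9%).
- Compound symmetry: v = (1 + 3×0.2)/4 = 0.40. Noncentrality 2.598; power 72.4% (normal 73.8%).

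The two-sided claim is matched by the AR(1) average. Compound symmetry reaches 80% only one-sided (normal 83.0%).

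**Step 2: the endpoint of 9.4.1 with the same inputs.** Under AR(1) the baseline-to-final correlation over three steps is 0.2³ = 0.008.

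| Contrast at completion | v | Power, t (normal) | Difference detectable at 80% |
|---|---|---|---|
| Raw change, r = 0.2 | 2(1 − 0.2) = 1.6 | 24.8% (25.4%) | 0.99 SD |
| Raw change, r = 0.008 | 2(1 − 0.008) = 1.984 | 20.9% (21.4%) | 1.10 SD |
| Completion score alone | 1 | 36.6% (37.6%) | 0.78 SD |
| Adjusted for baseline, r = 0.2 | 1 − 0.04 = 0.96 | 37.8% (38.9%) | 0.76 SD |
| Adjusted for baseline, r = 0.008 | 0.99994 | 36.5% (37.6%) | 0.78 SD |

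One-sided at 0.05, the raw change reaches about 31-36% and the completion contrasts about 49-51%.

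**Step 3: sensitivity to the correlation.** The values 0.5, 0.7 and 0.8 are assumptions, not from the documents. By the normal approximation, raw change has 38%, 56% and 74%; the baseline-adjusted completion score has 48%, 63% and 78%. To reach 80% at 0.45 SD, v must fall to about 0.333. That needs r of about 0.83 for change (1 − 0.333/2) or 0.82 for the adjusted score (√(1 − 0.333)).

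**Step 4: would a time-averaged primary contrast keep the 80%?** Section 10.1 schedules baseline and then monthly scores in the control arm. Participation is two months in 10.1 and three in 10.6, so about two or three post-baseline scores fall within it. For the mean of k post-baseline scores adjusted for baseline, v is the variance of that mean minus the square of its covariance with baseline:
- k = 2: v = 0.60 − 0.04 = 0.56 (compound symmetry) or 0.60 − 0.0144 = 0.586 (AR(1)); power 58% or 56%.
- k = 3: v = 0.467 − 0.04 = 0.427 or 0.431 − 0.007 = 0.424; power about 70% for both.
- k = 4: v = 0.40 − 0.04 = 0.36 or 0.336 − 0.004 = 0.332; power 76.8% or 80.0%.

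If baseline is itself one of the four averaged points, the arms are expected to be equal there, and a constant later effect of 0.45 averages to 0.75 × 0.45 = 0.34 SD. Power is then 48-55% (normal 50-57%).

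**The case against.** The strongest reply is that both sides of the mismatch are inferred. Section 11.2 never calls its contrast time-averaged, and the match depends on AR(1) and on the approximation used. A group-by-time F test with effect size f = 0.225 would also exceed 80% (88-91%). Section 9.4.1 lists measurements rather than a test: only its PHQ-9/GAD-7 item mentions the two groups. The mixed model in 11.1 belongs to the same family as the power model, so a time-averaged test is not excluded.

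Much of this stands. The contrast behind the 80%, its structure and its sidedness are reconstructions, and the baseline-to-final correlation is an extrapolation from one stated value. If 0.45 is read in SDs of the change, that comparison has about 37%, not 21-25%. But f = 0.225 in a group-by-time test is not a 0.45 SD mean difference, which is how 11.2 defines its effect. Fitting all scores in a mixed model does not give a before-to-after difference the variance of a four-score mean. No completion contrast examined at a correlation of 0.2 comes near 80%.

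Two stronger readings are tempting. A reader might infer that 11.2 contains an arithmetic slip; it need not, since its figure reproduces for a contrast it could have intended. A reader might also infer that the trial's true power has been shown to be 21-38%. The documents do not support that: they fix neither the primary contrast nor the correlation structure, and that range would pool raw change with different analyses of the completion score.

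**Conclusion.** The concern holds as a mismatch between the power statement and the primary endpoint. The stated 80% is consistent with a four-score average and cannot be tied to the before-versus-after endpoints. Under the working assumptions, power at 0.45 SD is about 21-25% for raw change and about 37-38% for the completion score, with or without baseline adjustment. The size of the shortfall depends heavily on the correlation, but these contrasts stay below 80% for assumed correlations up to 0.8. Dropout and the several primary scales, neither allowed for in 11.2, are left out of these figures; dropout would lower power further, as would any multiplicity adjustment.

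This does not show that 60 patients is the wrong number: 11.2 attributes the size mainly to workshop capacity. What needs correcting is the claim about what 60 patients can detect.

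**What to change.** Keep 60 patients. Name one primary between-arm contrast in 9.4.1 and 11.1, preferably baseline-adjusted. Restate power or detectable difference in 11.2 for that contrast, giving the correlation structure, the sidedness and the time-points used.

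- If the completion score stays primary, replace 80% at 0.45 SD with about 37% for the baseline-adjusted comparison, or a detectable difference of about 0.77 SD at 80% power, and state the 0.2 correlation on which this rests.
- If the mean of the post-baseline scores is made primary, amend 9.4.1 accordingly, keep the completion comparison as secondary, and recompute for the number of post-baseline scores actually scheduled in both arms (Step 4). Sections 10.1 and 10.6 must be reconciled on the length of participation first, because that fixes the number of scores.

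The cost is wording in three sections. No patients, visits or data are added; the stated power becomes less favourable.
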